4.4 End of Study Definition

The end of the study (EOS) is defined as the date when the last visit of the last participant has been achieved in all participating centers.

Last patient last visit (LPLV) of a participant is reached if he/she has completed the last scheduled procedure shown in the Schedule of Activities (this also includes phone contacts during long-term FU) unless the patient died or withdrew consent or is lost to FU.

The LPLV date may also be reached based on the last participant switching to a roll-over study or being switched to commercial drug supply with no cost to the participant.

Furthermore, to reach EOS, the following criteria need to be satisfied in this study:

- All participants have discontinued nivolumab treatment.
- The last included participant has been followed for at least 24 months since first study treatment administration.

If the study is stopped by the Sponsor but benefits are observed for ongoing participants, further treatment options may be discussed and agreed between the investigator, sponsor and the participant (for further information refer to Section 10.1.9).

Primary completion

The primary completion is defined by the event when all participants have been assessed for response rate (as defined by RECIST v1.1) by at least 5 post-baseline scans unless they have discontinued before due to progression or any other reason i.e., have been followed for approximately 10 months from 1st dose.

5. Study Population

Prospective approval of protocol deviations to recruitment and enrollment criteria, also known as protocol waivers or exemptions, is not permitted.

Recruitment has been stopped at 70 treated patients.

In Amendment 1, it was planned that approximately 143 participants would be screened to achieve 100 treated participants of which approximately 50-60 participants would have a left sided primary tumor. In order to allow appropriate balance of participants with right and left sided primary tumors, enrollment may be restricted to either left or right sided tumors during the study. (Information about right and left sided primary tumors of the participant will be recorded by the investigator or delegate in IxRS when the participant is registered in IxRS after signing off the PI/ICF.).

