Tumor assessments will be performed locally by participating radiologists/Investigators and whenever possible all scans taken at each clinical site will be interpreted by the same radiologist/Investigator at that site. Scans must meet the standard of care for imaging of lesions in the respective organ system(s). Unless progression is noted, all lesions will be assessed and reported at each scheduled scan.

All imaging scans (coded with study participant number and in digital imaging and communications in medicine [DICOM] format) as well as imaging-related adjunctive data (e.g., fluorodeoxyglucose [FDG] dose and tracer uptake time) must be prospectively collected and transferred to Bayer, or Bayer-designated imaging core lab, in case independent central review is needed.

The tumor markers CEA and CA 19-9 will be evaluated on an exploratory basis in participants with CRC and will not be used to assess objective tumor response.

Assessment of disease

RECIST v1.1 will be applied by the Investigator as the primary measure for categorization of disease on the baseline imaging and assessment of tumor response until progressive disease (see Section 10.7). CR and PR must be confirmed with repeated imaging performed at least 4 weeks after initial documentation of response.

iRECIST is based on RECIST v1.1, but adapted to account for the unique tumor response seen with immunotherapeutic drugs. iRECIST will be used by the Investigator to assess tumor response and progression, and make treatment decisions (see Section 10.8).

Tumor scans are required at screening, during study treatment and at the End of Treatment: see section 1.3 SoA Table 1–2. Tumor scans are also required during active follow-up, if applicable.

- Baseline assessments will be conducted during the screening period and target lesions should to be selected, measured, and recorded before start of study intervention. Scans that were obtained prior to the participant signing the ICF document for this study can be used as baseline assessments provided that they were performed within 28 d of starting study treatment and meet the requirements for the study

- Assessments during study treatment will be performed every 8 weeks (± 7 d) for the first year and every 12 weeks ± 14 d thereafter. Tumor assessment during the study intervention period includes the same anatomic areas as baseline and will be done until radiological disease progression or the end of the study.

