4. AE associated with an overdose or incorrect administration of study drug should be recorded on the AE eCRF.

Decisions regarding dose interruptions or modifications will be made by the investigator in consultation with the Medical Monitor based on the clinical evaluation of the participant.

For detailed guidance on overdosing please refer to the most current version of the nivolumab IB.

CCI

CCI

Timing: See SoA ([Table 1-2](#)) and Schedule of Biomarker Blood Sampling ([Table 1-3](#)) for

CCI
C..

CCI

9. Statistical Considerations

This is a single arm, Phase II study with ORR as primary endpoint. Background response rate for the combination is estimated to be at most 5%. Target response rate for the combination treatment will be 17%.

A one-sided exact binomial test will be conducted to test the hypothesis.

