9.2 Sample Size Determination

As of amendment 2, it is decided to stop recruitment at 70 treated patients. With this sample size of 70 patients, when the true underlying ORR is 17% or higher, and a baseline response rate of 5% is assumed, a one-sided exact binomial test at a type-I error of at approximately 2.5% would result in a power of 92.6%, with at least 8 responders needed to achieve significance.

The location of the primary tumor is a factor and it is expected that 40%-45% of patients will have the primary tumor on the right side. With 31 patients with right-sided tumors, the probability of observing 4 or more responders (ORR 13%) is approximately 80% when the true underlying response rate is 17%, and the probability of observing 2 or fewer responders (ORR 6.5%) is approximately 80% when the true ORR is 5%.

With 39 patients with left-sided tumors, the probability of observing 6 or more responders (ORR 15%) is approximately 67% when the true underlying response rate is 17%, and the probability of observing 2 or fewer responders (ORR 5.1%) is approximately 70% when the true ORR is 5%.

For this calculation SAS PROC POWER was used.

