6.2.2 Primary Endpoint: Overall response rate (ORR) based on RECIST v1.1

Primary endpoint for efficacy assessment is ORR per RECIST v1.1. Radiological tumor assessments will be done locally by the investigator.. ORR is defined as the percentage of subjects with complete response (CR) or partial response (PR) and will be analyzed after all participants met the criteria for primary completion, which is to have 5 post-baseline scans i.e., to have been followed for 10 months, or to have dropped out of the trial. The data base will then be locked for analysis.

The primary analysis of the primary endpoint will investigate the hypothesis

$H_0: \text{ORR}_{\text{Combination}} \leq 5\%$ versus

$H_1: \text{ORR}_{\text{Combination}} > 5\%$

The hypothesis will be tested by a one-sided exact binomial test, assuming a background response rate for the combination to be at most 5%. The target response rate for the combination treatment will be 17%. Using a one-sided exact binomial test at a type-I error of at most 2.5% at least 8 responders out of the 70 patients are needed to achieve significance.

The result of the exact binomial test will be presented in a table, giving the response rate, the number of responders needed, the number of responders observed, the test-statistic and the p-value. Inferential testing will not be repeated by subgroup, only confidence intervals will be presented for the subgroup analysis.

Further analysis of the primary endpoint includes frequency tables (with the ORR table also including all “Best overall response” categories) as well as corresponding 95% two-sided Clopper-Pearson confidence intervals. RECIST results will be displayed by visit as well. All descriptive analyses (incl. confidence intervals) of the primary endpoint will be repeated by two subgroups:

- primary tumor side (right and left). The information about tumor side does not come from the CRF, but is stored in the IxRS system and has to be transferred to the database. .
- ECOG performance status at baseline (0 vs 1)

Formal testing of ORR will not be done for these subgroups.

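### The lock rule makes no allowance for a response first seen at the fifth scan, which may still await confirmation when primary completion is declared

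*Protocol*

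**What the plan says.** Protocol 4.4 defines primary completion as the point when all participants have been "assessed for response rate (as defined by RECIST v1.1) by at least 5 post-baseline scans unless they have discontinued before" because of progression or any other reason, and equates this with roughly 10 months from first dose. SAP 6.2.2 gives the matching criterion, "which is to have 5 post-baseline scans i.e., to have been followed for 10 months, or to have dropped out of the trial", and then locks the database. Neither document states an interval between trigger and lock.

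Protocol 8.1 sets tumor assessments every 8 weeks (± 7 days) in the first year. It also states that "CR and PR must be confirmed with repeated imaging performed at least 4 weeks after initial documentation of response".

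The ORR definitions in Protocol 9.4.2 and SAP 6.2.2 count CR or PR and are silent on confirmation. SAP 4.6 keeps unscheduled visits out of the analysis and only lists them, without saying whether this covers tumor scans.

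The only confirmatory test is one count. According to SAP 6.2.2, "at a type-I error of at most 2.5% at least 8 responders out of the 70 patients are needed to achieve significance".

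**The concern.** The completion rule treats scan 5 as part of the window in which response is assessed, yet the confirmation rule needs a further scan after it. For participants treated early this does not matter, because they will have a sixth scan long before the last participant reaches the trigger. For those treated last, a CR or PR that first appears at scan 5 may still be awaiting its repeat scan when the database is locked. Nothing in either document holds the lock for such a case or says how the response would be classified.

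If only confirmed responses count, that participant is entered as a non-responder. If confirmation is not enforced, the same participant is a responder. With a threshold of 8, the classification of one participant can decide the trial, so it should be fixed before the data are seen.

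There is a related ambiguity in Protocol 4.4. Its waiver covers participants who discontinued, without saying whether from treatment or from the study. Protocol 4.1.3 and 8.1 keep scanning participants who stop treatment without progression. Under the treatment reading, such a participant could be counted as complete while a first PR was still waiting for its follow-up scan.

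**Working it through.** **1. The plan's own figures.** Inputs: n = 70, null ORR 5%, target ORR 17% (Protocol Sections 9 and 9.2), success at 8 or more responders. Exact binomial tails:

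- P(X ≥ 8 | 0.05) = 0.0234 and P(X ≥ 7 | 0.05) = 0.0604, so 8 is the right cut-off at 2.5% one-sided.
- P(X ≥ 8 | 0.17) = 0.9256. Protocol 9.2 says the design "would result in a power of 92.6%, with at least 8 responders needed to achieve significance"; this reproduces.

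**2. Timing.** Months are converted at 30.44 days (SAP 4.6).

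- Scan 5: 5 × 8 = week 40, day 280, 9.2 months (weeks 39–41 with the window).
- Ten months: 304.4 days, week 43.5.
- Earliest nominal confirmation: 40 + 4 = week 44, day 308, 10.1 months (weeks 43–45 with the scan 5 window).
- Next scheduled scan: week 48, day 336, 11.0 months.

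Nominal confirmation therefore falls about half a week after 10 months, and scheduled confirmation about a month after it.

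**3. Share of patients without the week-48 scan at lock (s).** The documents give no accrual curve. I assume uniform accrual over A months, with A at most 16.3: the dates in Protocol 12.1, 12 July 2019 to 18 November 2020, are 495 days apart, and 495/30.44 = 16.3. A = 10 and A = 6 are illustrations.

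| Lock when the last patient reaches | Formula | A = 16.3 | A = 10 | A = 6 |
|---|---|---|---|---|
| scan 5 (week 40) | (336 − 280)/(30.44 A) | 11.3% | 18.4% | 30.7% |
| 10 months | (336 − 304.4)/(30.44 A) | 6.4% | 10.4% | 17.3% |

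The range is about 6% to 31%. If an off-grid repeat at exactly 4 weeks counted, the numerators would fall to 28 and 3.6 days. The shares would then be 5.6–15.3% (28/(30.44 × 16.3) and 28/(30.44 × 6)) and 0.7–2.0% (3.6 over the same denominators).

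**4. Effect on the test.** Let q be the share of eventual confirmed responders who first respond at scan 5. The documents do not give it; I assume 5–10%. Taking response time as independent of entry date, expected responders lost = 70 × 0.17 × q × s = 11.9 q s, and the counted ORR is 0.17 × (1 − q s).

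| q | s | Counted ORR | Responders lost | Power |
|---|---|---|---|---|
| 5% | 6% | 16.95% | 0.04 | 92.4% |
| 5% | 31% | 16.74% | 0.18 | 91.7% |
| 10% | 6% | 16.90% | 0.07 | 92.2% |
| 10% | 31% | 16.47% | 0.37 | 90.8% |

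As a stress case, q = 20% with s = 20% loses 0.48 responders and leaves power at 90.3%.

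**5. When one loss matters.** Losing one responder changes the result only if exactly 8 would otherwise be counted: P(X = 8 | 0.17) = 6.3%. If exactly one responder were always lost, power would be P(X ≥ 9 | 0.17) = 86.2%. That is a bound, not an expectation.

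**6. Direction.** The loss can only reduce the counted rate, so type-I error falls. At q = 10%, s = 31% the null rate becomes 0.05 × (1 − 0.031) = 0.04845 and the rejection probability 0.0198, against 0.0234.

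**The case against.** A reader might infer that a scan-5 response cannot be confirmed and that a true responder is necessarily lost. The documents do not support that, for three reasons.

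- The trigger is trial-wide and a minimum. Only those treated near the end of accrual are exposed, and only if their first response comes at scan 5.
- Completion is also described as about 10 months. A scan 5 done at week 39 and repeated 4 weeks later gives week 43, just inside week 43.5. Lock may also come some time after the trigger.
- The loss presupposes that ORR counts confirmed responses. Protocol 9.4.2 and SAP 6.2.2 do not say so. Read literally, they would count an unconfirmed scan-5 PR, and nobody would be lost.

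A reader might also extend the discontinuation gap to both documents. SAP 4.2 defines drop-outs as leaving the study, and Protocol 1.2 treats active follow-up as being on study. Under the SAP, a participant with a pending PR in active follow-up has not dropped out, so the ambiguity sits in Protocol 4.4 alone.

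These limits stand, and they make the point conditional and small. They do not remove it. The 10-month wording accommodates only an early scan 5 with an off-grid repeat, and SAP 4.6 may exclude that repeat as unscheduled. An unstated gap before lock is not a rule. The silence on confirmation also conflicts with the mandatory wording of Protocol 8.1, which leaves a pending response to be classified after the data are known.

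**Conclusion.** The point holds in conditional form. If ORR means confirmed response, as Protocol 8.1 implies, the stated completion and lock rule may leave a late-treated participant with a first CR or PR at scan 5 unconfirmed and therefore counted as a non-responder.

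The expected size is about 0.04 to 0.37 responders out of 11.9, with power between 90.8% and 92.4% instead of 92.6%. This rests on two assumptions that the documents cannot settle: 5–10% of responders first responding at scan 5, and 6–31% of patients lacking the week-48 scan under uniform accrual. The error is conservative. The contrast between p = 0.023 at 8 of 70 and p = 0.060 at 7 of 70 is correct, but it applies to any single miscounted responder in this design and should not be read as the likely effect here. This is a clarification worth making before lock, not a flaw in sample size or error control.

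**What to change.** - **Protocol 4.4 and SAP 6.2.2:** for any participant with a first, unconfirmed CR or PR when the 5-scan/10-month criterion is met, primary completion is reached only after the confirmatory scan (at least 4 weeks later; the scheduled week-48 scan suffices), progression, or the end of tumor assessments.
- **Protocol 9.4.2 and SAP 6.2.2:** state that ORR counts confirmed CR and PR, consistent with Protocol 8.1, and that a confirmatory scan counts even if done at an unscheduled visit. Without this the first change may not affect the count.
- **Protocol 4.4:** replace the word *discontinued* with *ended tumor assessments*, which aligns it with the SAP's criterion of leaving the trial.

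The sample size, cut-off of 8, type-I error of 0.0234 and power of 0.9256 are unchanged, and no scan beyond the existing schedule is needed. The cost is a few sentences, plus a lock delay of about 4 to 8 weeks that arises only if a first response is pending.

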5.1 Inclusion Criteria

Participants are eligible to be included in the study only if all of the following criteria apply:

1. Capable of giving signed informed consent as described in Section 10.1.3 which includes compliance with the requirements and restrictions listed in the ICF and in this

protocol. A signed informed consent must be obtained prior to conducting any study-specific procedures.

2. Male and female adult participants 18 years of age or older on day of signing informed consent.
3. Histological or cytological confirmed advanced, metastatic, or progressive pMMR/MSS adenocarcinoma of colon or rectum.
 - a) Microsatellite status should be performed per local standard of practice. (e.g., IHC and/or PCR, next-generation sequencing). Only participants with pMMR/MSS mCRC are eligible.
4. Known extended RAS and BRAF status as per local standard of practice.
5. Participant must have progressed (radiologically or clinically) or been intolerant to no more than two (for extended RAS mutant) or three (for extended RAS wild type) lines of systemic chemotherapy regimens for advanced or metastatic CRC. Maintenance regimens, such as 5-fluorouracil or capecitabine, with or without bevacizumab, should not be counted as separate lines of treatment. Reintroduction of previously administered chemotherapy containing oxaliplatin, irinotecan or 5-fluorouracil/capecitabine, without newly added biologics like EGFR inhibitor for RAS wild type patients and locoregional treatments such as hepatic arterial infusion therapy or Yttrium-90 radioembolization should not be counted as separate lines of treatment.
 - Prior line of therapy must include ALL of the following agents
 - a) Fluoropyrimidines
 - b) Irinotecan
 - c) Oxaliplatin
 - d) anti-VEGF therapy, and, if extended RAS wild type, an anti-EGFR therapy (if appropriate and patient is eligible)
 - Patient must have evidence of progression on or after the last treatment regimen received and within 6 months prior to study enrollment
 - Patients who were intolerant to prior systemic chemotherapy regimens are eligible if there is documented evidence of clinically significant intolerance despite adequate supportive measures.
 - Adjuvant/neoadjuvant chemotherapy can be considered as one line of chemotherapy for advanced/metastatic disease if the participant had disease recurrence within 6 months of completion
6. ECOG (Eastern Cooperative Oncology Group) PS of 0 to 1.
7. Adequate hematologic and organ function as assessed by the following laboratory tests performed within 7 d before treatment initiation:
 - Total bilirubin ≤ 1.5 x the upper limit of normal (ULN). Total bilirubin (≤ 3 x ULN) is allowed if Gilbert's syndrome is documented.
 - Alanine transaminase (ALT) and aspartate aminotransferase (AST) ≤ 3 x ULN (≤ 5 x ULN for patients with liver involvement of their cancer)
 - Platelet count $\geq 100,000$ /mm³, Hemoglobin (Hb) ≥ 9 g/dL, WBC ≥ 2000 / μ L absolute neutrophil count (ANC) ≥ 1500 /mm³

- Serum creatinine $\leq 1.5 \times$ ULN or creatinine clearance ≥ 40 mL/min (measured or calculated using the Cockcroft-Gault formula)
 - Prothrombin time-international normalized ratio (PT/INR) < 2.3 and activated partial thromboplastin time (aPTT) $< 1.5 \times$ ULN.
8. Measurable disease as determined by RECIST v1.1
 9. Provision of recent tumor tissue (as defined below) is mandatory for all participants at screening (Formalin-fixed paraffin-embedded block or minimum of 20 slides).
 - Tumor tissue obtained within 180 d of enrollment and after the last dose of most recent anti-cancer therapy
 - Or a new biopsy

Exceptions for patients with less than required tumor tissues may be considered after documented discussion and approval by the sponsor.

10. Anticipated life expectancy greater than 3 months
11. Be able to swallow and absorb oral tablets.
12. Women of childbearing potential (WOCBP) must agree to follow instructions for method(s) of contraception for the duration of study intervention and 210 d after last dose of regorafenib and 5 months after the last dose of nivolumab.

Males who are sexually active with WOCBP must agree to follow instructions for method(s) of contraception for the duration of study intervention and 120 d after last dose of regorafenib. In addition, male participants must be willing to refrain from sperm donation during this time.

Contraceptive use by men or women should be consistent with local regulations regarding the methods of contraception for those participating in clinical studies. Please refer to Section 10.4 for more information.

5.2 Exclusion Criteria

Participants are excluded from the study if any of the following criteria apply:

1. Participants with dMMR/MSI-H colorectal cancer.
2. Prior therapy with regorafenib, anti-PD-1, PD-L1, or CTLA-4 inhibitors, or any form of immunotherapy to treat cancer
3. Systemic anti-cancer treatment within 14 d or less than 5 half-lives (whichever is shorter) of the first dose of study treatment
4. Has unresolved clinically significant toxicity of greater than or equal to National Cancer Institute Common Terminology Criteria for AEs (NCI-CTCAE, v5.0) Grade 2 attributed to any prior therapies (excluding anemia, lymphopenia, alopecia, skin pigmentation, and platinum-induced neurotoxicity)
5. Arterial thrombotic or embolic events such as cerebrovascular accident (including transient ischemic attacks) within 6 months before the start of study medication. Active pulmonary emboli or deep vein thrombosis that are significant or not adequately controlled on anticoagulation regimen
6. Congestive heart failure \geq New York Heart Association (NYHA) class 2

7. Unstable angina (angina symptoms at rest), new-onset angina (begun within the last 3 months), myocardial infarction less than 6 months before start of study drug
8. Uncontrolled cardiac arrhythmias
9. Poorly controlled hypertension, defined as a blood pressure consistently above 150/90 mmHg despite optimal medical management
10. Persistent proteinuria of NCI-CTCAE Grade 3. Urine dipstick result of 3+ or abnormal, based on type of urine test strip used, is allowed if protein excretion (estimated by urine protein/creatinine ratio on a random urine sample) is <3.5 g/24 hr
11. Major surgical procedure or significant traumatic injury within 28 d before start of study medication. Note: If participants received major surgery, they must have recovered adequately from the toxicity and/or complications from the intervention prior to starting therapy
12. Non-healing wound, non-healing ulcer, or non-healing bone fracture
13. Participants with evidence or history of any bleeding diathesis, irrespective of severity
14. Any hemorrhage or bleeding event \geq NCI-CTCAE Grade 3 within 28 d prior to the start of study medication
15. Significant acute gastrointestinal disorders with diarrhea as a major symptom e.g., Crohn's disease, malabsorption, or \geq NCI-CTCAE Grade 2 diarrhea of any etiology.
16. Participants with an active, known or suspected autoimmune disease. Participants with type I diabetes mellitus (T1DM), hypothyroidism only requiring hormone replacement, skin disorders (such as vitiligo, psoriasis, or alopecia) not requiring systemic treatment, or conditions not expected to recur in the absence of an external trigger are permitted to enroll.
17. Participants with a condition requiring systemic treatment with either corticosteroids (>10 mg daily prednisone equivalent) or other immunosuppressive medications within 14 d of start of study treatment. Inhaled or topical steroids, and adrenal replacement steroid doses >10 mg daily prednisone equivalent, are permitted in the absence of active autoimmune disease.
18. History of (non-infectious) pneumonitis that required steroids or current pneumonitis
19. History of interstitial lung disease
20. Subjects with previous malignancies (except non-melanoma skin cancers, and the following in situ cancers: bladder, gastric, colon, cervical/dysplasia, melanoma, or breast) are excluded unless a complete remission was achieved at least 3 years prior to study entry and no additional therapy is required or anticipated to be required during the study period.
21. Diagnosis of immunodeficiency or is receiving chronic systemic steroid therapy (in dosing exceeding 10 mg daily of prednisone equivalent) or any other form of immunosuppressive therapy.
22. Presence of symptomatic central nervous system (CNS) metastases, or CNS metastases that require local CNS-directed treatment (such as radiotherapy or surgery). Participants with stable CNS disease or previously treated lesions are eligible for study

entry. In addition, subjects must be either off corticosteroids, or on a stable or decreasing dose of 10 mg daily prednisone (or equivalent).

23. Ongoing infection > Grade 2 NCI-CTCAE requiring systemic therapy.
24. Known history of human immunodeficiency virus (HIV) infection (HIV 1/2 antibodies).
25. Any positive test result for hepatitis B virus (HBV) or hepatitis C virus (HCV) indicating presence of virus, e.g. Hepatitis B surface antigen (HBsAg, Australia antigen) positive, or Hepatitis C antibody (anti-HCV) positive (except if HCV-RNA negative).
26. Pregnancy or breast feeding.
27. Psychological, familial, or sociological condition potentially hampering compliance with the study protocol and FU schedule.
28. Previous treatment with live vaccine within 30 d of planned start of study drugs (seasonal flu vaccines that do not contain a live virus are permitted).
29. Known hypersensitivity to any of the study drugs, study drug classes, or excipients in the formulation.

